Kanglaite Reduce the Toxicity of Radiotherapy of Head and Neck Cancer Phase II Study

NCT03101514

January 6, 2017

Study Protocol and Statistical Analysis Plan

Patients

Patients aged 18–80 years with pathologically confirmed head and neck cancer receiving radical or postoperative radiotherapy and Karnofsky score greater than 80 points were eligible for recruitment. Patients who received radiotherapy only, radiotherapy concurrent with single-drug platinum chemotherapy, or induction chemotherapy with fewer than three cycles were eligible. Patients with a history of head and neck radiotherapy, distant metastases, and targeted drug or non-platinum drug chemotherapy during radiotherapy were excluded.

Treatments

All patients received 20 g Kanglaite (200 mL) daily, administered as an intravenous injection for 5 days a week, concurrently with radiotherapy. Kanglaite injection was used before or after radiotherapy, no time interval requirement between Kanglaite and radiotherapy. The dosage of radiotherapy was adjusted as follows: 70 Gy for gross tumors and positive lymph nodes, 66 Gy for tumor bed (operation bed), 60 Gy for high-risk lymph node drainage area, and 50 Gy for low-risk lymph node drainage area. Single fraction dose was 1.82–2.12 Gy for 5 days a week, once a day. Intensity-modulated radiation therapy was used and the radiotherapy planning system used was Eclipse 7.0. Recombinant human granulocyte colony-stimulating factor and antibiotics were not allowed as prophylactic treatments. After the final patient completed radiotherapy and observation data was recorded, the trial stopped.

Study end-points

Primary end-point was the incidence of radiation-induced mucositis. Secondary end-points were as follows: (i) blood toxicity, liver and kidney functions, and other toxic events; (ii) nutritional status, overall QOL, and QOL specifically related to head and neck.

All the end-points could be observed in the course of radiotherapy; therefore, long-term follow-up data may be reported in the future. After radiotherapy, patients

were evaluated for recurrence, metastases, and death every 3 months in the first 3 years, and every 6 months thereafter until death.

Evaluation of data

Acute toxicity indicators

Mucositis and the associated symptoms (manifested as pain, dysphagia, or dry mouth), blood cell count, liver and kidney functions, and other toxic events were assessed at baseline (before radiotherapy), every week during radiotherapy, and post radiotherapy. All adverse events were graded according to NCI Common Terminology Criteria for Adverse Events v4.0 (NCI-CTCAE4.0).

Mucositis in patients with head and neck cancer receiving radiotherapy usually occurs in the oral cavity, oropharynx, hypopharynx, and larynx. In NCI CTCAE4.0, grade 1 oral mucositis, pharyngeal mucositis, and laryngeal mucositis are defined as those causing mild discomfort in normal oral intake, requiring no intervention. Grade 2 mucositis is defined as that causing moderate pain, not interfering with oral intake, but altering oral intake. Grade 3 mucositis is defined as that causing severe pain, with severely altered eating/swallowing, requiring medical intervention. Grade 4 mucositis is defined as that with life-threatening consequences, requiring urgent intervention. Grade 5 mucositis is defined as that causing death.

Blood cell count, liver and kidney functions were assessed at baseline (before radiotherapy)—via blood test—every week during radiotherapy, and post radiotherapy. The lowest scores during radiotherapy were recorded and considered as data.

Nutritional status

Nutritional status was scored using the Patient-Generated Subjective Global Assessment (PG-SGA). The scores 0–1 is well-nourished or anabolic, scores 2–8 is suspected or moderate under-nutrition, score ≥ 9 is severely undernourished. The PG-SGA scores were recorded at baseline (before radiotherapy), every week during radiotherapy, and post radiotherapy. The highest PG-SGA scores recorded every week during the course of radiotherapy were used as the data obtained during

radiotherapy.

Therapeutic nutritional supports were provided based on the grade of dysphagia. Nutritional supports were divided into oro-enteral nutrition preparation, tube feeding, total parenteral nutrition, and separated nutrition infusion. Total parenteral nutrition was defined as a combination of amino acids, carbohydrates, and fats administered intravenously. Separate nutrition infusion was defined as intravenous administration of any one amino acid, carbohydrate, and fat. Nutritional treatment was not considered for those receiving nutritional treatment for less than 3 days or <10 kcal/kg per day.

Quality of life score

European Organization for Research and Treatment of Cancer (EORTC) QLQ-C30 questionnaire was used to evaluate the overall QOL. European Organization for Research and Treatment of Cancer QLQ-Head and Neck 35 (EORTC QLQ-H&N35) questionnaire was used to evaluate QOL specific for head and neck. Quality of life for each patient was assessed at baseline (before radiotherapy), every week during radiotherapy, and post radiotherapy using the EORTC QLQ-C30 and EORTC QLQ-H&N35 questionnaires. The QLQ-C30 and QLQ-H&N35 questionnaires were distributed to patients weekly during radiotherapy, and the lowest scores were recorded as data during radiotherapy. Using the EORTC Group scoring guidelines, each item of the QLQ-C30 and QLQ-H&N35 questionnaires was scored from 0 to 100. Higher scores for functions in QLQ-C30 implied a better quality of life; higher scores for the symptoms in QLQ-C30 and all items in QLQ-H&N35 indicated worsening quality of life.

Statistical analysis

Descriptive statistics were used to summarize patient baseline characteristics. Normally distributed data are reported as mean and standard deviation. Qualitative data are presented as number of observations and percentages. All statistical analyses were conducted using SPSS Statistics v. 18 (IBM Corporation, NY, USA). A two-tailed $p < 0.05$ was considered statistically significant.

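### A single lowest-value rule covers blood counts, liver tests and kidney tests, so it keeps the least abnormal week for any liver or kidney marker that rises with injury

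*Combined protocol and SAP*

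**What the plan says.** Under Study end-points, the first group of secondary end-points is "i) blood toxicity, liver and kidney functions, and other toxic events". Under Evaluation of data, Acute toxicity indicators, the sampling schedule reads "Blood cell count, liver and kidney functions were assessed at baseline (before radiotherapy)—via blood test—every week during radiotherapy, and post radiotherapy". The sentence straight after it is the reduction rule: "The lowest scores during radiotherapy were recorded and considered as data". It distinguishes no test from another. The plan names no liver or kidney analyte and gives no adverse direction for any laboratory measure.

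Three other statements bear on the point:

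- Earlier in the same section: "All adverse events were graded according to NCI Common Terminology Criteria for Adverse Events v4.0". Whether laboratory grades draw on every weekly result or only on the retained lowest one is not stated.
- Under Nutritional status, where a higher score is worse, the rule runs the other way: "The highest PG-SGA scores recorded every week during the course of radiotherapy were used as the data".
- Under Quality of life score, the lowest weekly score is kept for both questionnaires, although that section says higher is worse for the QLQ-C30 symptom scales and for every QLQ-H&N35 item.

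**The concern.** Reducing weekly results to one extreme value is meant to capture each patient's worst state on treatment. That works only if the extreme is taken in the adverse direction. For a marker that rises with injury (assumed examples: transaminases, bilirubin, urea, creatinine), the minimum is the least abnormal week. It is raised only if every weekly value is raised.

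The trial sets out to show reduced toxicity, and all patients receive the study drug, so there is no control arm in which the same understatement could cancel. A transient rise that settles before the post-radiotherapy sample would leave no trace in the laboratory summary. It would appear only if it had been graded separately as an adverse event.

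**Working it through.** The plan gives no laboratory figure to reproduce, so the check has a logical part and an illustration.

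**Direction.** For any series, min(x₁,…,x_k) ≤ x_j for every j. For a marker that is worse when high, the retained value can never exceed the worst week and equals it only if all weeks are equal. A made-up series in multiples of the upper limit of normal, 0.8, 0.9, 1.2, 2.0, 3.5, 2.5, 1.5, is recorded as 0.8. Its worst value is 3.5.

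**Number of weekly samples (from Treatments).** The inputs are "70 Gy for gross tumors and positive lymph nodes" and "Single fraction dose was 1.82–2.12 Gy for 5 days a week, once a day".

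- At 2.12 Gy: 70/2.12 = 33.0 fractions; 33/5 = 6.6 weeks.
- The same 33 fractions at 1.82 Gy give 33 × 1.82 = 60.06 Gy, matching the 60 Gy level.
- At 1.82 Gy throughout: 70/1.82 = 38.5 fractions; 38.5/5 = 7.7 weeks.

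The main illustration uses k = 6 or 7. A larger k makes the loss bigger.

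**How often the minimum hides a raised value (assumed inputs).** Let each weekly sample be raised with probability p (5% or 10%), with exchangeable latent-normal correlation ρ from 0.3 to 0.9. With c = Φ⁻¹(1 − p) and q(z) = 1 − Φ((c − √ρ·z)/√(1 − ρ)), averaging over z ~ N(0,1):

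- P(any week raised) = E[1 − (1 − q)^k]
- P(minimum raised) = P(all weeks raised) = E[q^k]
- share missed = 1 − P(all)/P(any)
- share missed after crediting a post-radiotherapy value from the same distribution = E[(1 − q){1 − (1 − q)^k − q^k}]/P(any)

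| k | ρ | p | Any week raised | Minimum raised | Missed | Missed, post-RT value credited |
|---|---|---|---|---|---|---|
| 7 | 0.3 | 0.05 | 0.2447 | 0.000056 | 99.98% | 88.8% |
| 7 | 0.3 | 0.10 | 0.4137 | 0.00042 | 99.9% | 83.1% |
| 6 | 0.6 | 0.10 | 0.2902 | 0.0081 | 97.2% | 71.9% |
| 6 | 0.8 | 0.10 | 0.2232 | 0.0244 | 89.1% | 59.3% |
| 6 | 0.9 | 0.05 | 0.0999 | 0.0174 | 82.6% | 53.4% |
| 6 | 0.9 | 0.10 | 0.1820 | 0.0414 | 77.3% | 47.5% |

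With k = 8, ρ = 0.9 and p = 0.10, the share missed rises to 81.2%.

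**Second check, on mean change from a single baseline value.** This simulation uses k = 7, independent weekly errors and within-patient SD = 1, all assumed except k.

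| True course | Lowest − baseline | Highest − baseline |
|---|---|---|
| No change | −1.35 SD | +1.35 SD |
| One week up by 3 SD | −1.27 SD | +3.04 SD |
| Linear rise to 3 SD | −0.13 SD | +3.56 SD |
| Linear rise to 5 SD | +0.36 SD | +5.35 SD |

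Under the stated rule, a one-week rise of 3 SD looks almost the same as no change. The first row also shows that either extreme drifts away from a single baseline value when nothing has happened. This affects how the corrected rule should be reported.

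**The case against.** The strongest reply is that the authors meant the worst value. Laboratory results are not scores, the lowest liver or kidney function is the worst function, and the nutrition rule does pick the worse direction. That reading is plausible, but the text does not support relying on it. The nutrition rule shows that the plan can state direction measure by measure. The quality-of-life rule keeps the lowest score on scales where the plan itself says higher is worse, which may be loose wording or the same slip again. An analyst following the sentence would take the minimum.

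The second reply is that CTCAE grading covers the gap. If grades use all weekly results, elevations that reach a grade are captured and the rule damages only a descriptive summary. This part stands as a possibility: the consequence depends on which values feed the grade, and the plan does not say.

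The third reply concerns the percentages. Prevalence, correlation and distribution are assumed, the model has no time trend, and CTCAE capture is credited at zero. At ρ = 0.95 (k = 6, p = 0.10) the share missed falls to 64%, and to 37% with the post-radiotherapy value credited. Injury that accumulates and persists would be seen more often in that last sample. These limits are fair. The figures illustrate how the rule behaves and do not estimate an effect in this trial; the conclusion does not rest on them.

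**Conclusion.** The concern holds. As written, the rule gives the wrong summary for any liver or kidney marker that rises with injury: the on-treatment value kept is the least abnormal one. That direction needs no assumption beyond the existence of such a marker among the tests done.

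The size is not known from the documents. Under the assumed inputs, 10.0-41.4% of patients have some raised on-treatment value, but only 0.006-4.1% have a raised minimum. CTCAE capture would lower the share missed by an amount that cannot be calculated here.

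The scope is limited to the liver and kidney part of secondary end-point (i). Blood counts, for which lowest is the adverse direction, and the mucositis primary end-point are not touched. It should be fixed, but it does not threaten the main result.

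**What to change.** Replace the single sentence with a rule that:

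1. lists each laboratory analyte and its adverse direction;
2. keeps the lowest on-treatment value for blood counts and for any measure that falls with injury, and the highest for any marker that rises;
3. states that CTCAE v4.0 laboratory grades use every weekly result, and reports the worst on-treatment grade per patient and analyte;
4. reports the post-radiotherapy value separately;
5. adds baseline-to-worst grade shift tables or week-by-week summaries, so that an extreme of 6 to 8 values is not read as a pure change from one baseline value.

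The lowest-score wording under Quality of life score should be checked at the same time, since it has the same form.

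The cost is a short change to the text and a re-derivation from the weekly results. If only minima were entered in the database, the values must be taken again from the source laboratory reports. Recorded liver and kidney toxicity may go up. Against a single baseline value, part of that increase would be selection of an extreme, which is why item 5 is needed.

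### The lowest blood value during radiotherapy is the datum and the use of baseline is not stated, so abnormalities that predate radiotherapy and persist may be counted as blood toxicity

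*Combined protocol and SAP*

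**What the plan says.** Secondary end-point (i), under Study end-points, is "blood toxicity, liver and kidney functions, and other toxic events". It is not limited to new or worsened findings.

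Under Evaluation of data, Acute toxicity indicators, the toxicity measures "were assessed at baseline (before radiotherapy), every week during radiotherapy, and post radiotherapy", with grading by CTCAE v4.0. For blood counts and liver and kidney tests, one further sentence fixes the on-treatment value: "The lowest scores during radiotherapy were recorded and considered as data". It does not mention the baseline result.

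Under Patients, the entry rule on prior treatment is "Patients who received radiotherapy only, radiotherapy concurrent with single-drug platinum chemotherapy, or induction chemotherapy with fewer than three cycles were eligible". Postoperative radiotherapy is also allowed. No blood-count, liver or kidney limit appears, and no interval from chemotherapy or surgery to radiotherapy. The exclusion of non-platinum drugs applies only during radiotherapy.

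Under Treatments, every patient receives Kanglaite with radiotherapy, and no control arm is described. Statistical analysis provides a descriptive summary of baseline characteristics, means with standard deviations, counts with percentages, and a two-sided 0.05 threshold. It names no change-from-baseline, paired or shift analysis.

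**The concern.** Some patients will reach radiotherapy after induction chemotherapy or an operation, and the entry rules do not prevent them from starting with a low count. Consider a patient who enters with grade 2 leukopenia and stays at grade 2, or recovers only to grade 1. The on-radiotherapy nadir is abnormal, and nothing in the plan stops it from being tabulated as blood toxicity, although nothing got worse on treatment.

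In a randomised comparison, carried-over abnormality would tend to balance between arms. Here it goes straight into the reported rate, and its size depends on how many induction and postoperative patients happen to be enrolled. The title's aim is reduced radiotherapy toxicity; a rate containing an unknown amount of pre-treatment abnormality is hard to read against that aim. Leaving the definition open also lets it be chosen after the results are seen.

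**Working it through.** **No figure to reproduce.** The documents give no sample size, expected toxicity rate or baseline prevalence, so the figures below are illustrations under stated assumptions.

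**Definitions**
- b: share of all patients abnormal at baseline and still abnormal at the on-radiotherapy nadir (assumed).
- w: share of those b patients who worsen by at least one grade (assumed).
- n: share of all patients who are normal at baseline and become abnormal on radiotherapy (assumed).

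Patients who are abnormal at baseline but normal at every on-radiotherapy sample count under neither rule.

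**Formulas**
- Incidence from the nadir alone = b + n.
- Incidence of new or worsened abnormality = bw + n.
- Excess = (b + n) − (bw + n) = b(1 − w). The new-onset share n cancels.

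**Worked example.** Take b = 20% and w = 20%, with the other 80% normal at baseline and 20% of them newly abnormal, so n = 0.80 × 0.20 = 16%.
- Nadir alone: 20% + 16% = 36%.
- New or worsened: 0.20 × 0.20 + 0.16 = 4% + 16% = 20%.
- Excess: 16 points, which equals 0.20 × (1 − 0.20).

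**Excess in percentage points over assumed ranges**

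| b | w = 0 | w = 20% | w = 40% |
|---|---|---|---|
| 10% | 10 | 8 | 6 |
| 20% | 20 | 16 | 12 |
| 30% | 30 | 24 | 18 |
| 40% | 40 | 32 | 24 |

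At b = 0 the two definitions agree.

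**How many values the nadir is drawn from.** At 70 Gy and the stated fraction sizes, 70 / 2.12 = 33.0 and 70 / 1.82 = 38.5 fractions. At five a week that is 6.6 to 7.7 weeks, or roughly 6 to 8 weekly samples. One abnormal sample is enough to make the nadir abnormal. If a patient's weekly values varied independently and normally about a constant level, the lowest of 6 to 8 would lie on average 1.27 to 1.42 within-patient standard deviations below that level (by simulation). A nadir set beside a single baseline value therefore falls somewhat even with no true change.

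**Direction of the rule.** The lowest value is the worst one for blood counts. For liver and kidney tests that rise with injury it is the best one. The excess above therefore describes blood counts; for rising tests, the same sentence would tend to miss toxicity.

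**The case against.** The strongest reply is that the plan is silent on baseline rather than dismissive of it. The sentence on lowest values can be read as only a data-reduction step, turning several weekly results into one on-treatment value. The Nutritional status and Quality of life score sections do the same, each taking an extreme weekly value as the on-treatment datum. With separate baseline, on-treatment and post-treatment phases, the on-treatment value could simply be shown beside the baseline one. This stands: a reader might infer that baseline is disregarded by rule, and the documents do not say so. What remains is that its use is unspecified, and a plan followed as written has nothing to keep persisting abnormalities out of the rate.

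Three other inferences also go too far.
- A reader might extend the lowest-value rule to pain, dysphagia and dry mouth. That sentence covers blood counts and liver and kidney tests only. The symptoms are introduced as manifestations of mucositis, with no counting rule given. Nor would baseline prevalence set a floor under the symptom rate, because symptoms can resolve.
- A reader might size the problem as the share given induction times the share of those with a low count at baseline. That assumes every abnormality persists to an on-radiotherapy sample and none worsens. A count that recovers before the first weekly sample is not captured, and a patient who worsens is an event under either definition.
- A reader might say the plan charges these abnormalities to Kanglaite. The end-point names blood toxicity without attributing it. With radiotherapy in all patients, platinum in some and no control arm, a baseline rule would not settle attribution.

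It is also fair that this concerns a secondary end-point, and that the primary mucositis end-point is not shown to be affected.

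**Conclusion.** The concern holds as a gap in the definition. The plan fixes the on-treatment blood value as the lowest one, leaves the role of baseline open, and admits patients whose counts may already be low. Persisting pre-radiotherapy abnormalities may therefore be reported as blood toxicity. That patients come to radiotherapy directly from chemotherapy or surgery is not stated; it is only not ruled out.

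The size is b(1 − w). Neither term is in the documents, so no single figure can be given: at b = 10% the excess is 6 to 10 points for w from 40% down to 0, it grows in proportion to b, and it vanishes if no baseline abnormality persists. These figures also assume that any abnormal grade is reported. If only higher grades were reported, b would be the share already at those grades, which would be no larger and probably smaller. This should be corrected because the correction is cheap, but it does not threaten the primary result.

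**What to change.** Replace the lowest-value sentence with a rule of this kind: *for each blood count and each liver and kidney test, the on-treatment result is the worst CTCAE grade during radiotherapy; a toxicity event is counted only if that grade is higher than the patient's own baseline grade.* Using worst grade instead of lowest value also corrects the direction for tests that rise with injury.

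Add a shift table of baseline grade against worst grade for each test, split by prior induction chemotherapy, prior surgery and concurrent platinum. The first two splits show where carry-over comes from; the third shows an allowed source of low counts during radiotherapy.

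The cost is one sentence and a set of tables from data already collected, with no new visit and no change to eligibility or treatment. There are two limits. A patient with a high baseline grade has less room to register worsening, which the shift table makes visible. And the worst of several weekly results is still set against one baseline result, so some apparent worsening will be chance; the report should say so.

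### The laboratory data rule keeps the lowest value during radiotherapy, which is the wrong extreme where high is abnormal and leaves out the scheduled post-radiotherapy value; mucositis has no rule at all

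*Combined protocol and SAP*

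**What the plan says.** All of this is in the combined protocol and SAP.

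- **Laboratory toxicity** (Evaluation of data, Acute toxicity indicators). Blood count and liver and kidney function are tested at baseline, "every week during radiotherapy, and post radiotherapy". The paragraph closes with the rule "The lowest scores during radiotherapy were recorded and considered as data". These variables are secondary end-points.
- **Mucositis** (same section). Mucositis, its symptoms and other toxic events "were assessed at baseline (before radiotherapy), every week during radiotherapy, and post radiotherapy". Adverse events are graded by CTCAE v4.0, where a higher grade is worse. No sentence says how repeated mucositis grades become one result per patient.
- **Primary end-point** (Study end-points). "Primary end-point was the incidence of radiation-induced mucositis", with no grade threshold and no time window. The section adds that "All the end-points could be observed in the course of radiotherapy", as the reason why long-term follow-up may be reported later.
- **Parallel rules.** For nutrition: "The highest PG-SGA scores recorded every week during the course of radiotherapy were used as the data obtained during" radiotherapy. For quality of life: "the lowest scores were recorded as data during radiotherapy".

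The time of the post-radiotherapy assessment is not given.

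**The concern.** A toxicity summary per patient needs three things: a direction, a window and a grading scale. The laboratory sentence gives a direction that suits blood counts only, and a window that ends before the last scheduled test. It does not say that the extreme value is then converted to a CTCAE grade.

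Two errors could follow. A patient with a raised liver or kidney marker would be represented by the most normal value on file. And a patient whose worst result appears at the post-radiotherapy test would be classed by an earlier, milder one. Both lead towards less recorded toxicity, in a trial whose title states the aim of reducing it. For the primary end-point, an analyst has no rule to follow and could choose the window after seeing the data.

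**Working it through.** The plan gives no sample size, target rate or event count, so it has no figure of its own to reproduce.

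**1. Direction.** Let a patient's weekly values be x1 to xk.
- Where low is abnormal (blood counts), the minimum is the worst value, and the rule is right.
- Where high is abnormal, the minimum is the best value. The datum exceeds an upper limit only if every weekly value exceeds it. A patient who is abnormal in all weeks but one is recorded as normal.
- If the word scores means CTCAE grades instead of raw values, the lowest is the mildest grade for every variable, blood counts included.

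The plan names no individual liver or kidney test. That at least one of them is abnormal when high is my assumption; transaminases and creatinine are the usual examples.

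**2. Number of visits.** The gross-tumour dose is 70 Gy, in fractions of 1.82–2.12 Gy, five a week.
- 70 / 2.12 = 33.02, so 34 fractions; 34 / 5 = 6.8 weeks.
- 70 / 1.82 = 38.5, so 39 fractions; 39 / 5 = 7.8 weeks.

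That gives about 7 to 8 weekly assessments before the post-radiotherapy one.

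**3. Sign of the window effect.** With values oriented so that high is bad, the maximum over the weekly visits cannot exceed the maximum over those visits plus one more. Leaving out the post-radiotherapy value therefore lowers a worst-grade rate or leaves it unchanged.

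**4. Size of the window effect, general form.** Let p be the incidence during radiotherapy, and q the chance that a patient event-free until then first reaches the grade at the post-radiotherapy assessment. The incidence including that assessment is p + (1 − p)q, so the understatement is (1 − p)q. Both p and q are assumed. Results are in percentage points.

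| p | q = 0 | q = 0.02 | q = 0.05 | q = 0.10 | q = 0.20 |
|---|---|---|---|---|---|
| 0.1 | 0 | 1.8 | 4.5 | 9.0 | 18.0 |
| 0.5 | 0 | 1.0 | 2.5 | 5.0 | 10.0 |
| 0.9 | 0 | 0.2 | 0.5 | 1.0 | 2.0 |

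**5. Size under a model of correlated visits.** Simulation of 400,000 patients, 7 weekly visits plus 1 post-radiotherapy visit, first-order autoregressive normal severity with correlation 0, 0.5, 0.8 or 0.9, and the threshold set so that 30% reach it over all 8 visits. All of these inputs are assumptions.

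| Course of severity | Rate over first 7 visits | Loss from 30% (points) |
|---|---|---|
| No trend | 26.8–28.1% | 1.9–3.2 |
| Worsening 0.1 SD per visit, post-radiotherapy included | 23.9–25.9% | 4.1–6.1 |
| Worsening 0.2 SD per visit, post-radiotherapy included | 20.7–23.1% | 6.9–9.3 |
| Post-radiotherapy mean 0.5 SD better than last week | – | 0.2–2.9 |
| Post-radiotherapy mean 1 SD better than last week | – | 0–1.0 |

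The last two rows span trends of 0 to 0.2 SD per visit during treatment. The two forms agree: the largest loss has p = 0.207, so q = (0.300 − 0.207) / (1 − 0.207) = 0.12.

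**The case against.** The strongest reply is that the sentence discards nothing. The nutrition and quality-of-life rules reduce weekly values to one during-treatment time point, beside separate baseline and post-radiotherapy assessments. The laboratory sentence may do the same, with post-radiotherapy values tabulated on their own. The documents do not exclude this reading, but no sentence states it for toxicity. Nor would it supply a worst grade per patient, because two separate percentages cannot be combined into one. It also leaves the direction error untouched. One could say that lowest was loosely meant as worst, but the nutrition rule says highest where high is bad, so the wording does depend on direction elsewhere.

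Three stronger readings are tempting and are not supported.

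- **That the primary end-point is understated by rule.** The sentence closes the laboratory paragraph and does not name mucositis. The remark in Study end-points says the end-points can be observed during treatment, not that only that period counts.
- **That the understatement is about 2 to 9 points.** That range comes only from models in which the post-radiotherapy visit is as bad as the last treatment week or worse. With recovery the loss can be close to zero.
- **That the omission favours the drug.** All patients receive Kanglaite, and the documents give no control arm, historical rate or target. Whether a shorter window flatters the drug depends on the window used for a comparator that is not described.

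**Conclusion.** The point holds in a limited form. For liver and kidney measures where high is abnormal, the literal rule picks the wrong extreme and would miss toxicity; this needs no model, only the assumption that at least one such measure is tested. For all the laboratory variables, the literal rule also prevents a worse post-radiotherapy value from setting the patient's worst grade. The effect on a worst-grade rate is one-directional, but the documents do not allow its size to be found. With an assumed 30% incidence over all visits it lies between about 0 points (recovery by the post-radiotherapy visit) and about 9 points (continued worsening). With other assumed rates the formula above gives other values, zero included.

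For mucositis the defect is a missing definition. It matters because this is the primary end-point, but no bias in it has been shown.

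**What to change.** Replace the laboratory sentence with a derivation along these lines: for each laboratory toxicity, the patient's value is the worst CTCAE v4.0 grade, taken in the harmful direction for that analyte, over all assessments from the first fraction through the scheduled post-radiotherapy assessment. List the analytes and the direction for each.

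Apply the same derivation to mucositis, so that the primary end-point has a stated per-patient summary and window. Report when the post-radiotherapy assessment took place relative to the last fraction, since the plan gives no date and its timing may differ between patients. Keep the during-radiotherapy-only figure as a secondary line; the gap between the two then shows how much the window matters in this trial.

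The cost is a change to the SAP wording and a small change to the derivation. The assessment is already scheduled, so no new visit is needed. The downside is that reported toxicity rates may be slightly higher.
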